- Physician diagnosis of ischemic heart disease, with prior myocardial infarction or coronary revascularization procedure
- Referral to the Cardiac Rehabilitation Program
- Epworth Sleepiness Scale $<$ 18
- Ability to provide informed consent

For continuing to randomization, the following additional inclusion criterion applies:

- Moderate to severe obstructive sleep apnea, defined as an apnea-hypopnea index \geq 15 events per hour, with $>$ 50% of events being obstructive apneas or hypopneas

Exclusion criteria:

- Poorly controlled hypertension (>170/>110), poorly controlled diabetes (HbA1c > 9.0), severe renal failure with estimated glomerular filtration rate <30 ml/min, prior stroke with functional impairment or other severe, uncontrolled medical problems that may impair ability to participate in the study exams, based on medical history and review of medical records
- Severe daytime sleepiness, defined as Epworth Sleepiness Scale score 18 or higher or a report of falling asleep driving during the previous year
- Awake resting oxyhemoglobin saturation <89%
- Pregnancy
- Current use of a positive airway pressure device (including continuous or bi-level positive airway)

Study Design

The proposed study is a randomized, parallel group study comparing 8 weeks of therapy with continuous positive airway pressure (CPAP) to an educational control for patients with comorbid obstructive sleep apnea and coronary heart disease undergoing a structured cardiac rehabilitation program. The primary study outcome measure, to be made at baseline and at end of the treatment period, is change in walking distance and speed as measured by 6 minute walk test, a valid and reproducible measure of functional capacity. The primary analysis will compare the active treatment group to the control group. Secondary outcome measures include measures of functional status and health related quality of life, and adherence to cardiac rehabilitation.

Sample Selection

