The primary approach to recruitment will be through mailing to all patients with a diagnosis of coronary heart disease referred to the Cardiac Rehabilitation Program at the VA Boston Healthcare System. All mailings will contain a cover letter explaining the purpose of the mailing and containing the key elements of informed consent. The letter will contain the Epworth Sleepiness Scale and several additional questions, including age and contact information. The Epworth Sleepiness Scale, the most widely used tool for self-report assessment of sleepiness, asks the subject to rate the likelihood of falling asleep in a number of common situations. It has good internal reliability and test-retest reliability. This scale will be used to identify patients with sleepiness so severe that it would preclude safe participation in the study (Epworth Sleepiness Scale score ≥ 18).

A stamped and addressed return envelope will be provided to return the questionnaire. A toll-free number will also be provided to allow patients to respond by telephone, should they prefer. All participants responding to the questionnaire by mail or telephone will be screened for eligibility, and potentially eligible subjects invited to attend a Screening Visit. In addition, the mailing will include an "opt-out" postcard for patients who do not wish to be further contacted. Patients who do not respond to the mailing either by responding to the questionnaire or returning an opt-out postcard will be contacted by telephone approximately 2 weeks after the mailing and invited to participate.

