Participants randomized to the CPAP Group will then be given an auto-titrating CPAP device with pressure range initially set at 4-20 cm H₂O pressure. The CPAP device is capable of wireless transmission of utilization and efficacy data. At the end of the first week of CPAP use, the utilization data will be reviewed by the Home Sleep Testing Coordinator, who will judge their acceptability based on usage for at least 4 hours/night for at least 5 nights and absence of excessive mask leak. At this time, the pressure profile will be reviewed and the 90th percentile pressure (i.e., the pressure that is exceeded only 10% of the time) will be identified and the CPAP device wirelessly reset to a pressure range of this 90th percentile pressure \pm 3 cm H₂O. The Coordinator will review utilization data again at weeks 2, 4 and 6. If adherence does not meet the above target, the Coordinator will call the participant to discuss ways to overcome barriers to adherence. This approach has been used successfully for evaluating CPAP utilization in the recently completed HeartBEAT Study.

Interim telephone contact

Following initiation of therapy, study staff will make telephone contact with each participant at weeks 2, 4 and 6 to identify any early problems with treatment adherence and to ascertain any adverse events. In particular, sleepiness will be re-assessed using the Epworth Sleepiness Scale and [name] will contact any patient whose Epworth Sleepiness Scale score is ≥ 16 or who provides a response of 2 or 3 on the item regarding drowsy driving.

Final study visit

After 8 weeks of intervention, participants will return for a final study visit, at which time all procedures performed at the baseline visit will be repeated, including anthropometry and the Epworth Sleepiness Scale. Measurements taken at the end of participation in the Cardiac Rehabilitation program, including 6 minute walk test results and responses to the WHODAS II questionnaire, will also be recorded.

Participants will also be asked to wear an Actigraph GT3X monitor for a period of 7 days (except when swimming or bathing). This will be used to assess the level of activity performed by the participant at home following completion of the Cardiac Rehabilitation program.

Following completion of study procedures, each participant will be encouraged to accept referral to a sleep specialist within the VA to discuss treatment of sleep apnea.

Statistical analysis

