It is possible that patients randomized to HLSE alone may not effectively be treated for their sleep apnea for the 8 weeks of the study. Untreated sleep apnea may place subjects at increased risk of motor vehicle and other accidents; however, in a study of 1105 patients with sleep apnea randomly assigned to CPAP or sham CPAP for 6 months (the Apnea Positive Pressure Long-term Efficacy Study), we had no episodes of motor vehicle accidents due to sleepiness using safety education and monitoring procedures similar to those of present study.

Protection against risks

All study personnel will be fully trained and credentialed in Human Subjects Protections. All research data will be collected on standardized research forms with de-identified ID numbers, without personal identifiers. Any data collected from medical records will be entered onto case report forms with only study ID numbers, excluding personal identifiers. Only study personnel will have access to research data, which is kept either in locked cabinets, in password-protected computers in locked offices, or on secure password-protected drives located behind the VA firewall. Research staff members that are no longer involved during the course of the study will have their access terminated. All personal data will be stored separately from de-identified research data, and will be stored in password-protected files behind the VA firewall or in locked cabinets within the VA. Records will be destroyed in accordance with the VA Record retention schedule.

All CPAP devices will be equipped with heated humidifiers to minimize drying, and attention will be paid at set-up to identifying a best-fit mask to minimize mask discomfort

and air leaks. Subjects will be contacted at weeks 2, 4 and 6 to identify any early problems with treatment and to ascertain any adverse events, in particular the onset of dangerous levels of sleepiness. Participants will be extensively counseled at the baseline visit on safety measures related to excessive sleepiness.

Potential Benefits of the proposed Research to Human Subjects and Others

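### The only sleepiness-related contact trigger on study uses likelihood ratings, so an actual episode of falling asleep driving can fail to meet it; separately, no adverse-event inquiry is scheduled after week 6

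*Combined protocol and SAP*

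**What the plan says.** **Entry.** The Exclusion criteria rule out "Severe daytime sleepiness, defined as Epworth Sleepiness Scale score 18 or higher or a report of falling asleep driving during the previous year". The two limbs are alternatives, so a reported episode excludes whatever the Epworth score. The protocol does not say how that report is obtained.

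**On study.** Under Interim telephone contact, staff call every participant at weeks 2, 4 and 6, ask about adverse events and repeat the Epworth. A study role then contacts any participant "whose Epworth Sleepiness Scale score is ≥ 16 or who provides a response of 2 or 3 on the item regarding drowsy driving". Initial Screening describes the Epworth as a scale that "asks the subject to rate the likelihood of falling asleep in a number of common situations".

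**Purpose of the calls.** Protection against risks says they are meant "to ascertain any adverse events, in particular the onset of dangerous levels of sleepiness". The same section provides for counselling on sleepiness safety at the baseline visit. Data Safety and Monitoring names the same three contact weeks, has the PI and staff review adverse events weekly, and provides for classification and reporting to the IRB.

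**Final visit.** After 8 weeks participants return, "at which time all procedures performed at the baseline visit will be repeated, including anthropometry and the Epworth Sleepiness Scale". Six-minute walk and WHODAS II results are recorded and actigraphy is worn. Afterwards, "each participant will be encouraged to accept referral to a sleep specialist within the VA to discuss treatment of sleep apnea".

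**The concern.** The protocol treats falling asleep while driving as serious enough to bar someone from the trial. Once a participant is randomized, the rule that obliges someone to make contact looks only at how likely the participant thinks dozing is, not at whether it has happened. The two can diverge: a person may have one episode and still rate the likelihood low.

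The risk at issue is one the protocol names itself. Potential Risks states, in discussing participants left on education alone, that "Untreated sleep apnea may place subjects at increased risk of motor vehicle and other accidents". The gap applies to both arms but matters most for controls, who receive no CPAP. What is at stake is detecting and handling individual safety events, not the treatment comparison.

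A second, separate point concerns timing. If the last planned adverse-event inquiry is at week 6 and the visit after week 8 has none, events in the closing weeks are recorded only if someone volunteers them or they come to light some other way.

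**Working it through.** The first point is a check of one rule against another. The second is simple arithmetic on the schedule. The plan gives no figure of its own to reproduce.

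**1. Entry rule against on-study rule**

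Entry excludes if the Epworth total is 18 or more, or an episode of falling asleep driving in the previous year is reported. The on-study trigger is met if the total is 16 or more, or the driving item is 2 or 3.

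| Case | Entry (this criterion) | On-study trigger |
|---|---|---|
| Total 18 or more | Excluded | Met |
| Total 16 or 17, no episode | Not excluded | Met |
| Total 15 or less, driving item 2 or 3, no episode | Not excluded | Met |
| Total 15 or less, driving item 0 or 1, **has fallen asleep driving** | **Excluded** | **Not met** |

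In the last row, 15 or less fails the first limb of the trigger and 0 or 1 fails the second. The on-study rule is the more cautious one in rows two and three and the less cautious one in row four.

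**2. Does another stated contact rule cover the last row?**

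- The Treatment section has the Coordinator call when CPAP use misses its target. This concerns usage, in the CPAP arm only.
- Data Safety and Monitoring has the participant contacted when the PI's weekly data review shows physiological findings that warrant it. A report of dozing at the wheel is not such a finding.

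Neither covers the case.

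**3. What happens if the participant mentions the episode on a call?**

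It can be taken as an adverse event, reviewed at the weekly meeting, classified and reported to the IRB as its class requires. No direct question about falling asleep at the wheel is stated, and nothing on that route requires contact with the participant.

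**4. Adverse-event inquiry after week 6**

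Inputs: last listed inquiry at week 6 (Interim telephone contact; Data Safety and Monitoring); final visit after 8 weeks (Final study visit); 25 participants per arm (Overview).

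- Weeks without a scheduled inquiry: 8 − 6 = 2, and 2 / 8 = 25%.
- Both arms, if all complete: 50 × 2 = 100 of 50 × 8 = 400 participant-weeks.
- Control arm alone: 25 × 2 = 50 of 25 × 8 = 200 participant-weeks.

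Repeating the baseline procedures does not close this interval, because the baseline visit lists no adverse-event inquiry either. The Epworth is repeated at the final visit, but the contact trigger is stated only under the interim calls, so a high score at week 8 has no stated action.

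**The case against.** The case on the other side is substantial.

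- **Monitoring is stricter than entry in two respects.** The total-score cut-off is 16 rather than 18, and a driving-item cut-off is added. This stands: a reader might infer that on-study monitoring is generally laxer than screening, and the documents do not support that.
- **Other contact triggers exist.** A reader might infer that the Epworth rule is the only on-study trigger of any kind. It is not, given the CPAP-adherence call and the contact for physiological findings. It is the only one related to sleepiness.
- **An episode does not go unanswered.** A reader might infer that the plan has no response to a dozing episode. The calls are aimed at dangerous sleepiness among other events, review is weekly, and classification and IRB reporting follow. Baseline counselling on sleepiness safety applies to both arms. What is missing is narrower: a direct question and a required contact.
- **The cited experience is reassuring.** For a study of 1105 patients followed for 6 months, Potential Risks reports that "we had no episodes of motor vehicle accidents due to sleepiness using safety education and monitoring procedures similar to those of present study". This counts accidents. It gives no rate for episodes without an accident, so it neither sizes the gap nor shows that it is empty.
- **Question-level wording may sit elsewhere.** Call scripts and case report forms are not among the documents and may already hold such a question. That is possible, but the protocol does not require it.
- **Contact is described as frequent throughout participation.** The safety section says so, but the contacts it then names are weeks 2, 4 and 6. The referral encouraged at exit offers care and does not record an event.

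It is also fair to say that monitoring need not mirror an exclusion criterion. The case for change rests on its low cost, not on any breach of a standard.

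**Conclusion.** The point holds in a limited form, as a **minor** matter of safety monitoring. The only stated sleepiness-related contact trigger can be unmet by a participant in either arm who has fallen asleep driving, although that event excludes at entry. The episode may still be picked up and reviewed as an adverse event, but nothing requires that it be asked about directly or that the participant be contacted. Separately, about 2 of 8 weeks (25%) have no scheduled adverse-event inquiry, and the final-visit Epworth has no action attached.

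The group that slips past the trigger is narrow: an actual episode, a driving item of 0 or 1, and a total of 15 or less. Its size cannot be derived from the documents. A reader might infer that controls face a measurable excess of accidents from this gap; nothing in the documents supports or quantifies that.

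The 25% takes the 8-week duration given under Study Design and Final study visit, and the participant-week counts also assume no dropout. The Overview's three months, if it governed, would lengthen the interval. The primary analysis of six-minute walk distance is unaffected.

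**What to change.** 1. At the week 2, 4 and 6 calls and at the final visit, ask both arms: since the last contact, have you fallen asleep while driving, or had any vehicle or other accident?
2. Make a yes a third trigger for the contact already described under Interim telephone contact.
3. Apply all three triggers at the final visit as well as at the calls.
4. Add an adverse-event inquiry to the final visit, and list it in Data Safety and Monitoring.

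The cost is one question at four existing contacts (50 × 4 = 200 short answers if all complete), one inquiry at an existing visit, and a wording amendment. No new staff or procedure is needed. The downside is slightly longer contacts and a few extra calls, some of them for minor events. Putting the same question to both arms does not in itself reveal assignment to blinded staff.

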Coronary heart disease is the leading cause of death in the United States and a major cause of disability. Cardiac rehabilitation programs that include an exercise training intervention have been shown to reduce cardiac mortality by approximately 25%, with improved exercise tolerance and peak oxygen consumption, and a concomitant improvement in functional status and quality of life. Unfortunately, many patients entering cardiac rehabilitation programs do not complete them, and the increase in exercise capacity among completers is variable. Although psychosocial factors are important predictors of successful cardiac rehabilitation, one common but often undiagnosed barrier to successful rehabilitation is the presence of obstructive sleep apnea (OSA), which is highly prevalent in patients with coronary heart disease. Obstructive sleep apnea is a common condition in adults, associated with recurrent airway collapse during sleep resulting in intermittent hypoxemia and sleep fragmentation. Two studies of OSA in patients undergoing cardiac rehabilitation suggest prevalence in excess of 50%. While OSA is strongly associated with obesity, studies of exercise training in patients with OSA demonstrate a poorer response to exercise independent of body habitus. The sleepiness and fatigue caused by OSA may contribute to impaired motivation to exercise, although intermittent hypoxia itself has been shown to decrease ventilatory efficiency in healthy adults. Patients with OSA have reduced exercise tolerance compared to obese controls, and treatment of OSA with continuous positive airway pressure (CPAP) results in increased peak oxygen consumption on symptom-limited exercise testing and an increase in constant load exercise time. These studies suggest that treatment of OSA might substantially improve the response to exercise training as part of cardiac rehabilitation, although

these were uncontrolled case series in general patients with OSA, not in the setting of cardiac rehabilitation.

(b) Hypothesis

We hypothesize that identification and treatment of obstructive sleep apnea (OSA) in patients with comorbid OSA and coronary heart disease undergoing cardiac rehabilitation will improve their response to rehabilitation.

(c) Specific Objectives

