Coronary heart disease remains a leading cause of morbidity and mortality among veterans treated in the VA Health Care System (17, 18). Cardiac rehabilitation programs that include an exercise training intervention have been shown to reduce cardiac mortality by approximately 25% (1), with improved exercise tolerance and peak oxygen consumption, and a concomitant improvement in functional status and quality of life. Sleep apnea is a common co-morbid condition in patient with coronary heart disease and may be a barrier to effective cardiac rehabilitation. Determining the impact of sleep apnea treatment in patients with comorbid coronary heart disease and OSA, who undergo cardiac rehabilitation is therefore of great relevance to Veterans Health.

(3) Work Protocol

Overview

The proposed study is a randomized, parallel group study comparing three months of therapy with continuous positive airway pressure (CPAP) to an educational control for patients with comorbid obstructive sleep apnea and coronary heart disease undergoing a structured cardiac rehabilitation program. The study will be conducted over 2 years and participants will be recruited from among patients seen at the VA Boston Healthcare Systems with a diagnosis of coronary heart disease and referred to the Cardiac Rehabilitation Program. A total of approximately 150 patients will be recruited in order to randomize 25 patients to each group (CPAP or Control). Participation of an individual subject will be approximately 1 week for subjects not meeting criteria for randomization, and 8-10 weeks for subjects randomized. Participants will be age 18 and over, of either gender, have a diagnosis of coronary heart disease, and be referred to the Cardiac Rehabilitation Program at the VA Boston Healthcare System. No children or other special classes of individuals will be enrolled. All enrolled subjects will be veterans.

Study procedures will include:

- Screening Questionnaires (Epworth Sleepiness Scale)
- Portable Sleep Monitoring
- Baseline (Randomization) Visit, including:
 - Anthropometry
 - Randomization to treatment with one of the following two treatments:
 - Healthy Lifestyle and Sleep Education alone (HLSE)
 - HLSE plus CPAP (CPAP)
- Interim Telephone Contacts
- Final Study Visit
 - Anthropometry
 - Epworth Sleepiness Scale
 - 7 day actigraphy recording

Inclusion criteria for sleep apnea screening:

- Age \geq 18 years

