Baseline data will be summarized using standard descriptive statistics for demographic and baseline clinical characteristics by treatment group. Based on our experience with the HeartBEAT Study, the rate of dropouts during the course of the three-month trial is expected to be low and we do not expect dropouts to be differential with respect to treatment group assignment. The main analysis will include all subjects completing the follow-up examination. For the purposes of a sensitivity analysis, a result of “no change” will be imputed for all dropouts, and compared to the main analysis.

The analysis for the primary outcome measure will consist of a one-factor analysis of variance comparing the mean changes from baseline in six minute walk distance. The primary analysis is a simple analysis of variance, with data transformation or adoption of rank-based inference if approximate normality is not present. A p value <0.05 will be considered statistically significant. While the randomization should achieve approximate balance on potentially confounding conditions, analysis of covariance models that employ adjustments for age, sex, sleep apnea severity, comorbid illness, smoking and alcohol use will be fit to potentially improve the efficiency of the treatment effect estimates. Should a significant difference between treatment and comparator be identified, further exploratory analyses will assess the relation of adherence to CPAP therapy to change in outcome measures.

Each of the secondary outcome measures is continuous; therefore, analysis of these variables will be treated in a similar fashion to the analysis of the primary study endpoints.

Sample size and power

Our primary goal is to determine the impact of identification and treatment of obstructive sleep apnea in patients with coronary heart disease undergoing cardiac rehabilitation. Patients will be allocated into the two groups, HLSE or HLSE plus CPAP, randomly according to a 1:1 ratio.

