There are no published data on the effect of CPAP therapy on 6-minute walk distance in patients with coronary heart disease; however, in a recent report from a general sample of patients with OSA, treatment with CPAP was associated with a mean 114 m improvement in 6-minute walk distance after 4 weeks, compared to a control group not treated with CPAP (22). This is well above the minimal clinically important difference of 23 m in 6-minute walk distance reported for patients with stable coronary heart disease (23). The standard deviation in 6-minute walk distance in patients with stable coronary

heart disease has been estimated at 104 m (24), similar to the 90 m estimated for healthy adults (25). Assuming a modest correlation of 0.4 between repeated measures of the 6-minute walk test, the sample size of 25 subjects in each group will have 80% power to detect a difference between groups of 57 m in 6-minute walk distance, half of the difference reported for the effect of OSA treatment (22).

Human Subjects

Potential Risks

The study procedures do not place the subjects at risk of harm or discomfort greater than those encountered in routine medical care. Portable sleep monitoring may lead to minor sleep disturbance and some subjects may experience mild skin irritation from the sensors or electrodes used. The administration of questionnaires may be stressful, although none ask sensitive information.

The study treatment is generally considered quite safe. CPAP is a FDA-approved therapy for the treatment of sleep apnea. The use can be associated with a number of minor side effects, including nasal congestion, runny nose, dry nose or mouth, skin irritation from the mask or headgear, aerophagia or discomfort from the mask or air pressure. Rarely, sinus problems may get worse while using CPAP and mild nose bleeds may occur. These side effects will be minimized by using a humidifier built into the device and by using the most appropriate pressure.

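### The power statement treats all 25 randomised patients per group as analysed and allows for no loss; its 80% does not follow from the plan's own inputs even if nobody is lost

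*Combined protocol and SAP*

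**What the plan says.** Both Overview sections set the number randomised at 25 per group. Sample size and power uses the same number: "the sample size of 25 subjects in each group will have 80% power to detect a difference between groups of 57 m". Its inputs are a walk-distance SD of 104 m in stable coronary disease (90 m in healthy adults) and a correlation of 0.4 between repeated walks.

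Under Statistical analysis, the primary test is a one-factor analysis of variance on change in walk distance, at the 0.05 level. The main analysis is limited to patients with a completed follow-up examination. On attrition, the section says that "the rate of dropouts during the course of the three-month trial is expected to be low", based on the HeartBEAT Study, and that loss should not differ by group. A sensitivity analysis imputes no change for dropouts. No loss rate is given.

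Under Final study visit, the outcome data are described as "Measurements taken at the end of participation in the Cardiac Rehabilitation program, including 6 minute walk test results". The baseline walk is likewise taken from the rehabilitation note (Cardiac Rehab Assessment Measures). The Statement of the Problem says that "many patients entering cardiac rehabilitation programs do not complete them", and the Background repeats the point.

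**The concern.** The power statement is written for patients randomised, but the analysis will be done on patients with a completed follow-up. These numbers agree only if nobody is lost, and the plan itself expects some loss.

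The support for low dropout is also indirect. No rate from the earlier study is quoted, and nothing explains why retention there predicts whether an end-of-programme walk will be available here. Because the walk is drawn from programme records, a patient could stay in the trial and still lack the primary outcome after leaving rehabilitation.

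At stake is how a non-significant result is read. A reader who believes the trial had 80% power for 57 m would take a null result as fairly strong evidence against an effect of that size.

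**Working it through.** **Inputs.** From Sample size and power: 25 per group, difference 57 m, SD 104 m, r = 0.4. From Statistical analysis: change-score ANOVA, alpha 0.05. Sidedness is not stated, but a two-group ANOVA F test is equivalent to a two-sided t test. Loss rates are assumptions.

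**Step 1: reproduce the plan's figure at zero loss.**
- SD of change = SD × √(2(1 − r)) = 104 × √1.2 = 113.9 m.
- Standard error of the difference = 113.9 × √(2/25) = 32.2 m.
- Noncentrality = 57 / 32.2 = 1.77, against a critical t of 2.01 on 48 df.
- Power (noncentral t) = 41.1%; difference detectable with 80% power = 92.1 m. The normal approximation gives 42.4% and 90.3 m.

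The stated 80% is not reproduced. Other readings, all two-sided by noncentral t at zero loss, also fall short:
- SD 90 m, change score: 51.7%.
- SD 104 m, adjusting for baseline walk, residual SD = 104 × √(1 − 0.4²) = 95.3 m: 54.5%.
- SD 90 m, adjusting for baseline walk: 66.8%.

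Figures near 80% appear only under calculations that do not match the planned analysis. One uses SD × √(1 − r), which drops the factor of 2 under the root (80.6 m from 104 m, one-sided; or 69.7 m from 90 m, two-sided). Another is a one-sided baseline-adjusted test with the healthy-adult SD.

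**Step 2: SD implied by the stated power.** By noncentral t, 80% for 57 m at 25 per group needs an SD of change of 70.5 m. With SD 104 m this means r = 1 − (70.5/104)²/2 = 0.77, not 0.4.

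**Step 3: add loss.** Both bases use the noncentral t with n = patients analysed per group.

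| Analysed per group | Loss | Stated 80% taken as given (SD 70.5 m): power; detectable | Plan's inputs (SD 113.9 m): power; detectable |
|---|---|---|---|
| 25 | 0% | 80.0%; 57.0 m | 41.1%; 92.1 m |
| 24 | 4% | 78.3%; 58.2 m | 39.6%; 94.1 m |
| 23 | 8% | 76.5%; 59.5 m | 38.2%; 96.2 m |
| 22 | 12% | 74.6%; 60.9 m | 36.8%; 98.5 m |
| 20 | 20% | 70.3%; 64.1 m | 33.8%; 103.6 m |
| 18 | 28% | 65.4%; 67.8 m | 30.8%; 109.5 m |
| 17 | 32% | 62.8%; 69.8 m | 29.3%; 112.9 m |

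A 10% loss leaves 22-23 per group and a 30% loss leaves 17-18. At 20% loss, power falls by about 10 points on the first basis (80.0 − 70.3) and about 7 on the second (41.1 − 33.8). The base calculation alone accounts for about 39 points (80.0 − 41.1).

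**The case against.** The plan does not ignore dropout. It names a source for its expectation, predicts non-differential loss and specifies a sensitivity analysis. If loss really is low, the cost is small: one patient per group takes 80% to about 78%. Nothing in the documents favours 20% or 30% over a low rate. All of this stands, except that imputing no change in a sensitivity analysis does not restore the power claimed for the completers-only main analysis.

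A reader might infer that the rationale flatly contradicts the low-dropout expectation. It does not. The rationale and Background describe rehabilitation patients in general, while Statistical analysis concerns consented trial participants, who are telephoned at weeks 2, 4 and 6. Both statements can be true. Adherence to rehabilitation is itself a secondary outcome, so the plan allows for participants who attend poorly and are still followed.

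A reader might also equate leaving rehabilitation with a missing primary outcome. Study Design places the measurement at the end of the treatment period, and Final study visit refers to the end of participation in the programme, which is not the same as completing it. The documents do not say whether early leavers have an exit walk. Leaving early may remove the outcome; it need not.

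**Conclusion.** The point holds. The number randomised is used as the number analysed, the main analysis excludes patients without follow-up, and no loss is allowed for. The earlier study's low dropout does not by itself show that an end-of-programme walk will be available.

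A tempting reading is that the 80% is correct so long as nobody is lost. The plan's own figures do not support that: they give about 41% power and 92 m detectable at zero loss. The first set of powers in the table (78%, 75-76%, 70%, 63-65%) is therefore conditional on a figure that does not reproduce, and should not be quoted as this trial's power. On the plan's inputs, power is about 37-38% with 96-99 m detectable at 10% loss, 34% and 104 m at 20%, and 29-31% and 110-113 m at 30%.

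These results assume a two-sided test, equal loss in the two groups and the stated loss rates, none of which the documents supply as numbers. Attrition is the smaller of the two problems, but correcting the SD and correlation alone would still leave a power figure that is too high once anyone is lost.

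**What to change.** In Sample size and power, first correct the base calculation so that the SD of change, correlation, sidedness and planned test agree with the stated power. Then give power and detectable difference for the number expected to have a final walk, over a stated range of loss such as 10%, 20% and 30%. Adding loss scenarios to the uncorrected 80% would only repeat the error.

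In Statistical analysis, support the dropout expectation with the expected proportion of randomised patients without an end-of-programme walk. The local programme's completion data are one input; they are not the same quantity, since trial participants may be retained better and early leavers may still be tested.

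The cost is a few sentences and a look-up of programme records. The number randomised need not change for the statement to be accurate. The downside is a less favourable stated power.
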